After self-report questionnaires are completed, participants will then complete the baseline clinical interview (paper version of “LIMBIX - Measure - MINI Neuropsychiatric Interview.pdf”) conducted by a study team member who is not the ultimate research therapist. The clinical interview will generally take about 15 to 25 minutes. This interview will be videotaped to conduct reliability assessment on the diagnoses.

Participants who meet the study eligibility criteria will next be contacted by phone by another study team member within a week to receive their random assignment to either the virtual reality exposure therapy condition or the waitlist control condition and to schedule their treatment planning session. Participants in the immediate treatment group will be invited to start treatment soon after the baseline assessments, whereas those in the waitlist control condition will be invited to start this treatment 8 weeks later. The script “LIMBIX - Scripts - Study Therapist to Subject” will be used to facilitate this process.

Within a day the intake assessor completes the initial assessment for an eligible participant, the coordinator will (1) randomly assign the eligible participant who had just completed the interview to their treatment condition, (2) call the participant to inform them of their study condition, and (3) inform their research therapist assigned to be in charge with conducting the 8 to 10 50-minute weekly treatment planning and therapy sessions.

As participants assigned to the treatment condition will begin therapy immediately, the coordinator will communicate this message to the research therapist within a day of the initial assessment.

On the other hand, participants assigned to the waitlist control condition will begin therapy 8 weeks later, and the coordinator will communicate this message within a few weeks after the initial assessment visit.

Once the research therapist receives the message from the coordinator to start scheduling treatment with a particular participant, he or she is expected to contact the participant and set up an appointment within the next one or two weeks depending on their availability.

Step 3: Treatment Planning

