Once participants have been assigned their treatment condition and research therapist, they will be assessed for interest in beginning the specific job interview intervention or the general social settings intervention (“LIMBIX - Scripts - Treatment Selection - V1.docx”). Whereas the specific job interview intervention helps clients overcome their social phobia linked to job application situations, the general social settings interventions assists with helping clients overcome social fears across a variety of social situations (e.g., dating, ordering a cup of coffee at a cafeteria).

All treatment offered within the context of the study will be supervised by a licensed mental health provider and an advanced graduate student ([name] and [name]), and treatment options will be based on current best practices and available evidence-based care. Treatment will be based on exposure therapy, which has been shown through prior research to be effective for social anxiety disorder (Powers & Emmelkamp, 2008). In addition, therapy may focus on helping the participant to build a set of adaptive coping and emotion regulation skills, such as self-monitoring, breathing training, and enhancing motivation to take interpersonal risks.

The research therapist will determine if the intervention best matches the participant's presenting concerns and goals and will record this on the treatment plan. The VR treatment is tailored to participants' presenting problems (general social anxiety or job interview phobia). These plans will first be reviewed in supervision to ensure participants are offered treatment based on current best practices and standards of care. Treatment plans will also be reviewed with the participant to ensure agreement on the treatment plan and to allow for collaborative changes to the plan, as needed. Considerations such as the participant's digital literacy, comfort with technology, access to the tools, and participants' stated preferences will be considered.

Each 50-minute therapy session will be video recorded as part of the clinical supervision and research procedures to ensure that the research therapists adhere to the protocol of the virtual reality exposure therapy. The tapes will be coded by trained assessors to ensure quality of therapy and adherence. These videos will only be made available to the PI and study team members to maintain participants' confidentiality.

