8.0 Participant Numbers and Statistical Plan

8.1 Number of Participants

Indicate the total number of participants to be accrued.

If applicable, distinguish between the number of participants who are expected to be enrolled and screened, and the number of participants needed to complete the research procedures (i.e., numbers of participants excluding screen failures.)

750 participants

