8.2 Sample size determination

If applicable, provide a justification of the sample size outlined in section 8.1 – to include reflections on, or calculations of, the power of the study.

The proposed study is focused on examining the efficacy, acceptability, feasibility, and the experience of the patient when using virtual reality in treating job interview phobia. The number of participants (300 per intervention condition; 300 General Social Skills Training; 300 Job Interview Phobia; 150 Waitlist Control) was based on Kampmann et al. (2016) who conducted a virtual reality study with adults with social phobia and used similar primary outcome measures. In their study, their power calculations estimated that 300 participants/per intervention group would be sufficient to find significant differences (two sided-power, power= 80%, alpha -0.05, G*Power 3.2) based on an effect size of exposure therapy found in a meta-analysis (Powers et al., 2008).

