8.3 Statistical methods

Describe the statistical methods (or non-statistical methods of analysis) that will be employed.

We will conduct a series of growth curve analyses to test for treatment efficacy. We will use the R packages 'lme4' (Bates, Maechler, & Bolker, 2012), 'lmerTest' (Kuznetsova & Brockhoff, 2014), and 'lavaan' (Rosseel, 2012) to calculate the growth trajectories for each participants. We will test for the impact of time using participants' scores at post-treatment, and at 6-month and 12-month follow-ups. We intend to perform separate models for each of the study outcome measures.

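### The growth models in section 8.3 specify no therapist effect, so the comparison of VRET with still-untreated waitlist participants will have too small a standard error if outcomes cluster by therapist.

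*Combined protocol and SAP*

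**What the plan says.** Section 7.2 (Study Procedures) ties each participant to one therapist. After randomisation the coordinator is to "inform their research therapist assigned to be in charge with conducting the 8 to 10 50-minute weekly treatment planning and therapy sessions". The treatment-planning step begins "Once participants have been assigned their treatment condition and research therapist". The therapist also judges whether the intervention suits the participant and records the treatment plan. Beyond the virtual scenarios, "therapy may focus on helping the participant to build a set of adaptive coping and emotion regulation skills". Treatment length within the 8 to 10 sessions depends partly on the therapist's judgement. Waitlist participants wait 8 weeks and are then offered the same treatment.

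Section 8.3 (Statistical methods) is the whole analysis plan. It names lme4, lmerTest and lavaan, and says they will be used to "calculate the growth trajectories for each participants", with a separate model for each outcome. It gives no model formula, random-effects structure, therapist term or cluster adjustment. Section 8.1 sets the total at "750 participants" and section 8.2 divides it as "300 General Social Skills Training; 300 Job Interview Phobia; 150 Waitlist Control". Neither section allows for clustering.

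**The concern.** Participants treated by the same person share that person's skill, manner and judgement, so their outcomes may be correlated. Hypothesis 1 sets VRET against waitlist. While the waitlist arm is untreated, any such correlation sits in the treated arm alone; this is a partially nested design. A model that counts the 600 treated participants as independent then overstates the information in that arm. Confidence intervals come out too narrow and the 5% test rejects a true null hypothesis too often. Generalisation to other therapists is also overstated. Large caseloads matter here: 600 participants spread over a modest team means dozens per therapist, and a small ICC is multiplied by the caseload.

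**Working it through.** **Inputs from the documents.** Section 8.2 gives the allocation 300 : 300 : 150, which is 600 VRET against 150 waitlist when the two VRET arms are pooled. The test settings are printed as "two sided-power, power= 80%, alpha -0.05, G*Power 3.2", read here as two-sided alpha 0.05 and 80% power. The effect size is described only as "based on an effect size of exposure therapy found in a meta-analysis", with no value and no standard deviation.

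**Assumptions.** Number of therapists K (5 to 40), therapist ICC (0 to 0.10), equal caseloads, and total variance 1 in both arms.

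**The plan's own figure.** The 300 per group cannot be reproduced without an effect size, but it can be solved backwards. From n = 2(1.960 + 0.842)²/d² with n = 300, d = √(2 × 7.849/300) = 0.229. This value, about 0.23, is implied by the sample size and is not stated in the plan.

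**Standard error during the wait, 600 v 150.**
- Therapist ignored: variance = 1/600 + 1/150 = 0.008333, SE = 0.0913.
- Therapist clustering in the treated arm only: variance = [1 + (m − 1) × ICC]/600 + 1/150, with m = 600/K.
- True type I error of the nominal 5% test = 2 × [1 − Φ(1.96/r)], where r = true SE / reported SE.

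For K = 10 (m = 60):
- ICC 0.01: design effect 1 + 59 × 0.01 = 1.59; variance 1.59/600 + 1/150 = 0.009317; r = √(0.009317/0.008333) = 1.06.
- ICC 0.05: design effect 1 + 59 × 0.05 = 3.95; variance 0.013250; r = 1.26.

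| Therapists | ICC | r | True type I error |
|---|---|---|---|
| any | 0 | 1.00 | 5.0% |
| 40 | 0.01 | 1.01 | 5.3% |
| 40 | 0.05 | 1.07 | 6.6% |
| 20 | 0.01 | 1.03 | 5.7% |
| 20 | 0.05 | 1.14 | 8.4% |
| 10 | 0.01 | 1.06 | 6.4% |
| 10 | 0.05 | 1.26 | 12.0% |
| 6 | 0.01 | 1.09 | 7.3% |
| 6 | 0.05 | 1.41 | 16.5% |
| 5 | 0.10 | 1.84 | 28.6% |

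A simulation of 4,000 trials analysed without therapist gave 6.4% (ICC 0.01) and 11.9% (ICC 0.05) for K = 10, in agreement with the formula.

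**Power with the correct standard error, K = 10, d = 0.229.** Power = Φ(d/SE − 1.96). It is 71% with no clustering (SE 0.0913), 66% at ICC 0.01 (SE 0.0965) and 51% at ICC 0.05 (SE 0.1151). These are upper limits, because few therapists also means few degrees of freedom.

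**After the waitlist arm has been treated.** Suppose both arms use the same therapists, with balanced caseloads and the same therapist effects in each arm. The therapist effect then drops out of the arm difference, and the true variance is (1 − ICC)(1/600 + 1/150). The ratio r is √(1 − ICC), which is 0.995 to 0.975 for ICC 0.01 to 0.05. Type I error is 4.9% to 4.4%, slightly conservative.

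**The case against.** Four points can be made on the other side.

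1. **Section 8.3 does not exclude a therapist effect.** This is correct. A reader might infer that the models carry participant-level effects only. The section states no random-effects structure, and lme4 can fit a therapist term. What can be said is that none is specified.

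2. **The waitlist arm does get therapists.** This is also correct. A reader might infer that waitlist participants never have one, but section 7.2 starts their treatment after 8 weeks. The time points that section 8.3 names (post-treatment and later follow-ups) come after that, and no assessment at the end of the wait is described. At those time points the inflation shown above does not apply if the arms share therapists. The objection does not dispose of Hypothesis 1, because a comparison with an untreated waitlist has to be made while the waitlist is untreated.

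3. **Delivery is scripted.** Section 7.2 casts the team member mainly as a facilitator, with session and homework scripts, supervised plans and taped sessions coded for adherence. All this may keep the ICC low, so the documents do not show that the standard error is certainly too small. The therapist nevertheless keeps discretion over the plan, coping skills and treatment length, and the ICC cannot be known in advance.

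4. **A therapist intercept does not protect a slope.** This holds. With complete, balanced data, an intercept that is constant over time leaves the standard error of a slope or arm-by-time contrast unchanged. Such contrasts need a therapist-by-time term.

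**Conclusion.** The point stands in a conditional form. Section 8.3 specifies no therapist effect although each treated participant has one assigned therapist. For any comparison of VRET with still-untreated waitlist participants, the reported standard error is too small if the therapist ICC exceeds zero. With 10 therapists and ICC 0.01 to 0.05 the true standard error is 6% to 26% larger than reported, and type I error is 6.4% to 12.0%. With many therapists and a low ICC the effect is negligible, and at ICC 0 there is none. The size rests on assumed values for the number of therapists and the ICC; the power figures rest also on the assumed effect of about 0.23. The finding does not extend to comparisons made after both arms have been treated by the same therapists. It is worth acting on because it bears on the main hypothesis, and because a therapist term added after the results are seen would be post hoc.

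**What to change.** Record therapist identity for every treated participant. In section 8.3, write out the lme4 models with a therapist random effect switched on by a time-varying indicator that equals 1 for observations during or after treatment in either arm and 0 otherwise, for example `(0 + treated_it | therapist)`. The indicator must vary by observation: if it coded the randomised arm, it would leave out the therapists who later treat the waitlist arm. Where the tested contrast is a slope, add a therapist-by-time term. Use the Satterthwaite degrees of freedom from lmerTest. Report the number of therapists, their caseloads and the estimated ICC.

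The cost is one data field, one or two random terms in software the plan already names, and somewhat wider intervals. With few therapists the therapist variance will be imprecisely estimated, which is a further reason to report caseloads and the ICC.

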1.0 Objectives

22.1 Study Objectives

Describe the purpose, specific aims or objectives. State the hypotheses to be tested.

The purpose of this study is to test the efficacy of virtual reality videos to facilitate exposure therapy in social anxiety disorder (SAD). The exposure therapy videos are the focus of this experiment. Essentially, we are testing the efficacy of the Virtual Reality Exposure Therapy (VRET) scripts (i.e., virtual scenarios, people, and interactions that we expose socially anxious people to). To this end, the goal of the current study is to help people with social anxiety overcome their phobias. Individuals who experience a difficult time building social relationships, accomplishing everyday tasks, or pursuing interviews can practice those same behaviors in a controlled environment.

The study hypotheses are as follows:

1. Virtual reality exposure therapy intervention (vs. waitlist control condition) is effective for treating SAD symptoms.
2. Participants who received the virtual reality exposure therapy will experience maintenance of treatment gains following 3-month and 6-month post-termination of treatment.
3. Users of the virtual reality exposure therapy will demonstrate high amounts of acceptability of the treatment.

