22.2 Primary Study Endpoints

State the primary endpoints to be measured in the study. Clinical trials typically have a primary objective or endpoint. Additional objectives and endpoints are secondary. The endpoints (or outcomes), determined for each study subject, are the quantitative measurements required by the objectives. Measuring the selected endpoints is the goal of a trial (examples: response rate and survival).

To answer these questions, the proposed study will use both qualitative and quantitative methods. Qualitative methods will include a semi-structured interview at the end of the study to gather information on the participant's experience, as well as data collected throughout the therapy process. Quantitatively, the study proposes to use basic descriptive statistics to examine treatment outcomes and engagement with digital tools.

This exploratory study will answer the following questions:

- 1) Compared to the waitlist control condition, is the virtual reality exposure intervention more effective for treating symptoms of social anxiety disorder?
- 2) Are there higher treatment gains maintained over time among participants who receive the virtual reality exposure therapy compared to the waitlist control condition?

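### Section 8.3 specifies no comparison of VRET with the randomised waitlist; the only effect it names for testing is time

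*Combined protocol and SAP*

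**What the plan says.** Hypothesis 1 (22.1 Study Objectives) is a between-arm statement: "Virtual reality exposure therapy intervention (vs. waitlist control condition) is effective for treating SAD symptoms". The first primary question (22.2 Primary Study Endpoints) asks the same: "Compared to the waitlist control condition, is the virtual reality exposure intervention more effective for treating symptoms of social anxiety disorder". Section 7.2, Step 2, describes "random assignment to either the virtual reality exposure therapy condition or the waitlist control condition", and section 7.1 says that VRET will be compared with a waitlist group.

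Section 8.3 is the only statistical-methods text. It opens with "We will conduct a series of growth curve analyses to test for treatment efficacy", names three R packages, and continues: "We will test for the impact of time using participants' scores at post-treatment", to which it adds the scores at 6 and 12 months. It ends with "We intend to perform separate models for each of the study outcome measures". It gives no list of predictors, and it mentions neither arm, waitlist, interaction nor contrast. The only other analysis text, in 22.2, is that "the study proposes to use basic descriptive statistics to examine treatment outcomes and engagement with digital tools".

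**The concern.** A test of time asks whether scores change within participants. Hypothesis 1 asks whether they change more under VRET than under waiting. Within-participant change also carries natural course, outside care (section 7.1 lets participants seek it) and, once a baseline score is included, regression to the mean, since the subject-pool route in section 4.1 selects on high screening scores. The waitlist was randomised so that these could be subtracted out, and the effect named in section 8.3 does not do so.

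At stake is the primary conclusion. An analyst who follows section 8.3 literally gets a p-value that does not answer Hypothesis 1. One who adds arm on their own initiative must still choose between a slope and a visit contrast, decide whether to use baseline, pick the visit, and settle how the VRET conditions are set against waitlist. For a primary analysis these choices should be fixed before outcomes are seen.

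**Working it through.** **1. Texts side by side.** The objective, the primary question and the randomisation are all VRET versus waitlist. The analysis text names time only, at post-treatment and two later visits. Nothing elsewhere supplies a between-arm model. There is no stated effect estimate to reproduce; the sample size adds up (section 8.2: 300 + 300 + 150 = 750, the total in section 8.1).

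**2. A time test on the scores that section 8.3 lists.** A trend over post-treatment and follow-up scores depends only on differences among those scores.
- If VRET produces a benefit B by post-treatment and B is fully held, the mean is the same at all three visits. The expected slope is 0 whatever the size of B, so the test rejects at its nominal 5%.
- If both arms drift equally after post-treatment, the slope is not zero although VRET minus waitlist is zero.

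**3. Illustration if baseline were added.** Section 8.3 does not list baseline, so this shows how a time-only test behaves in the usual pre-post setting and does not predict the result of the plan as written.

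Inputs from the documents: N = 750; two-sided 5% (section 8.2). Assumptions, because the documents give no figures: a shared improvement c, in SD units, in both arms; pre-post correlation ρ from 0.3 to 0.7; no VRET effect.

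SD of change = √(2(1 − ρ)); SE = SD of change / √750; rejection probability ≈ Φ(c/SE − 1.96), the other tail being negligible.

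For c = 0.1:

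| ρ | SD of change | SE | c/SE | Time-only test rejects |
|---|---|---|---|---|
| 0.3 | 1.183 | 0.0432 | 2.31 | 64% |
| 0.5 | 1.000 | 0.0365 | 2.74 | 78% |
| 0.7 | 0.775 | 0.0283 | 3.54 | 94% |

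The same formula gives 21% to 42% at c = 0.05 and at least 99.6% at c = 0.2.

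For the arm-by-time contrast the expected difference in change is c − c = 0, so it rejects at 5% whatever c is. Simulation (4,000 trials per setting, 600 v 150, ρ = 0.5 and 0.7, c from 0 to 0.3) gave 4.4% to 5.6% for this contrast. The time-only test at c = 0.1 gave 78% and 93%.

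**The case against.** The strongest reply is that arm is implied. Section 7.1 states the intent to compare, and a growth-curve test of treatment efficacy could tacitly include an arm term. The sentence on time covers post-treatment onward, which is the window of Hypothesis 2, so it may describe the maintenance analysis and not the efficacy test.

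Much of this stands. A reader might infer that the arms will never be compared; the documents do not support that, because the intent is stated. Nor does section 8.3 write out a model without arm: it writes out no model. But if the time sentence serves Hypothesis 2, Hypothesis 1 has no specified test at all. On either reading the between-arm contrast is missing.

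A reader might also infer that improvement from baseline common to both arms would be declared a VRET effect at the rates tabulated. That goes too far, because those rates need a baseline score that section 8.3 does not list. With the listed scores, shared change completed before post-treatment cannot enter the test, and the clearer failure is that a held benefit goes undetected.

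Finally, this point says nothing about whether 750 participants are enough. Section 8.2 gives no effect size, and power against the waitlist is a question of allocation, separate from the missing contrast.

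**Conclusion.** The point holds as an omission in the primary analysis: section 8.3 specifies no between-arm comparison, and the one effect it names does not answer Hypothesis 1 or the primary questions. That follows from the text alone, as does the inability of a time test on post-treatment and later scores to detect a gain that is already made and then held.

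The 64% to 94% figure is conditional. It assumes an added baseline, an equal 0.1 SD improvement in both arms, a correlation of 0.3 to 0.7 and complete data on 750 participants. It shows that a modest shared change is enough to make a time-only test misleading at this sample size.

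This should be corrected before any outcome data are analysed. It is separate from the mismatch between the 6- and 12-month visits in section 8.3 and the 3- and 6-month visits in sections 7.1 and 7.2: correcting the visits would still leave a test of time.

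**What to change.** In section 8.3, make the test of Hypothesis 1 the VRET-minus-waitlist difference in change from baseline, by randomised assignment, at the end of the 8-week waiting period. The mixed-model package already named can fit it: score ~ visit + arm + arm:visit + (1 | participant), with visit categorical and baseline included. The arm-by-visit coefficient at 8 weeks is the test. Later visits cannot serve, because the waitlist is offered VRET from 8 weeks and no untreated control remains. Label time effects after that point as descriptive of maintenance and not as evidence of efficacy.

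Define arm. Section 22.4.3 randomises to three conditions, whereas section 7.2 describes two and settles the type of VRET in Step 3 with regard to the participant's interest. These must be reconciled. Then state whether the two VRET conditions are pooled against waitlist, or compared with it separately under multiplicity control. Separate comparisons are randomised ones only if section 22.4.3 describes what is done.

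The cost is rewording and a few lines of code, plus one item of data collection. The documents describe no assessment of the waitlist between baseline and its own VRET: section 7.2, Step 5, exempts it from between-session measures until treatment starts, and Step 7 ties final assessments to termination. The investigators should confirm or add the existing online self-report packet for both arms at about 8 weeks, before the waitlist begins VRET. With 8 to 10 weekly sessions and one or two weeks to arrange the first, some VRET participants will still be in treatment then. The plan should say that the contrast is at a fixed time from baseline and includes them.
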